8.4 Risk Mitigation

The Osia 2 System has been designed and manufactured to ensure that all risks have been reduced as far as possible; however, as with any surgical intervention, a 100% success rate cannot be guaranteed. As such, the following will be performed during the clinical study to further mitigate the risks identified above:

- Before start of each site in the clinical study each investigator will have done documented surgery training according to the Cochlear Osia OSI200 Implant Physician's Guide either at a cadaver lab or on a plastic skull.
- The suggested surgical approach and the two new tools have been validated by 27 surgeons in 4 regions and will be described in a usability report under preparation by the time of this final CIP (6).
- CBAS qualified staff will be present during one or more of the first surgeries at each clinic in order to support any surgical questions or issues related to the OSI200 Implant.
- All reported ADEs and DDs will be reviewed regularly by the Sponsor for the duration of the study to facilitate early detection and appropriate intervention if events are unanticipated with respect to incidence, severity, or outcome.
- MRI examinations can be performed safely on a person with this implanted device only under very specific conditions. An MRI information package is supplied with each implant for additional information regarding magnetic resonance imaging (19). Subjects enrolled in the study that receive the Osia 2 System will receive an MRI card, for information to radiologists if an evaluation and planning of any MRI examination becomes necessary. Subjects that have received radiation therapy, or are planned for radiation therapy during the study, at the same side of the skull where the Osia 2 System will be positioned are excluded from the study.
- Users shall routinely check the device for signs of overheating and for signs of discomfort or skin irritation at the implant site and inform the study staff.
- Do not apply continued pressure to the processor when in contact with the skin (e.g. sleeping while lying on processor, or using tight fitting headwear).

8.5 Risk-to-Benefit Rationale

The Investigational device has been designed to make the implant more robust, reduce complexity of the surgery and provide a more advance sound processor compared to the precursor Osia System. The predecessor system has been shown to be safe and effective in a multicentre clinical investigation.

As with the predecessor device, most of the risks identified for the Investigational device are related to surgery and/or implant failures leading to explantation (further details are provided in the Investigator's Brochure).

The design modifications to the Investigational device compared to the predecessor implant (OSI100), as described above, have resulted in a more robust implant thought to reduce the occurrence rate / likelihood of implant failures leading to explantation. In addition, the shorter and less complex surgical procedure required for Investigational device implantation is believed to mitigate the general risks associated with surgery and general anaesthesia.

Based on the data presented herein, the relatively low risk associated with the intended use of the device, and the added benefit to the patient, it is believed that the anticipated risks related

to the intended use of the Investigational device are well within the acceptable limits when weighed against the benefits to the patient.

9 STATISTICAL CONSIDERATIONS

9.1 General Considerations

The distribution of continuous variables as well as change in continuous variables will be given as n, mean, SD, SEM, Median, Min and Max and the distribution of dichotomous and categorical variables will be given as number and percentages. For continuous variables estimated mean and the 95% two-sided confidence interval (bootstrapped) for difference between groups will be presented.

Since all included subjects will have measurements of the primary and important secondary efficacy variables for unaided hearing, with the Investigational device and with a Baha Power sound processor on a Baha Softband, all statistical analyses will be paired. All statistical analyses will be non-parametric. In order to choose the most powerful test, the Fisher's non-parametric permutation test for paired observations will be used for all paired analyses of continuous variables. The permutation tests use the measured values and not only the ranks in the calculations. For paired analysis of dichotomous and ordered categorical variables the Sign test will be used.

The main efficacy analyses will be performed at 3 months after surgery on the ITT population and complementary efficacy analyses will be performed 6 months after surgery on the ITT population. In addition, all analyses will be made on the PP population. Sub analyses will also be performed on one group consisting of Mixed/conductive subjects and one consisting of SSD subjects.

Imputation of missing values will be performed for all efficacy variables using stochastic regression imputations. All ITT analyses will be performed/presented both for the imputed and for the non-imputed data (sensitivity analyses).

The final definition of the analysis sets (ITT, PP and Safety) will be taken at the clean file meeting before database lock. See separate paragraph for definitions.

A statistical analysis plan (SAP) with detailed statistical analyses specified for all variables and time points will be written and signed before the database lock.

The approximate number of subjects per site is 10 and the maximum is approximately 15. See separate paragraph for Sample size calculation.

Major protocol deviations are those that are considered to have an effect on the analysis. The number of patients with major protocol deviations will be summarised per treatment group. A list of protocol deviations will be produced.

Imputation of missing values will be performed for all efficacy variables. No imputation of baseline values or baseline carry forward will be made. Imputations will be made according to the following rules:

1. If a value is missing at the end of a patient, last observation will be carried forward.
2. If a missing value is occurring between two time points with values, an interpolation will be made for continuous variables and for categorical variables the value from the previous visit will be carried forward.

The number of patients with major protocol deviations will be summarised per treatment group. A list of all protocol deviations will be produced.

9.2 Outcome measures

9.2.1 Primary Outcome measures

The improvement in hearing performance when using the Investigational device at 3 months post-surgery compared to the preoperative unaided situation assessed as:

- Thresholds audiometry, free-field [PTA4, mean of 0.5, 1, 2 and 4 kHz].
- Adaptive speech in noise [speech-to-noise ratio, 50% speech understanding].

9.2.2 Secondary Outcome measures

- The improvement in hearing performance at fitting and 6 months post-surgery when using the Investigational device compared to the unaided situation assessed as:
 - The improvement in Thresholds audiometry, free-field [PTA4, mean of 0.5, 1, 2 and 4 kHz]
 - The improvement in Adaptive speech in noise [signal-to-noise ratio, 50% speech understanding].
- The improvement in hearing performance at fitting, 3- and 6 months post-surgery when using the Investigational device compared to the unaided situation assessed as:
 - The improvement in Thresholds audiometry, free-field [0.25, 0.5, 0.75, 1.0, 1.5, 2.0, 3.0, 4.0, 6.0 and 8.0 kHz].
 - The improvement in Speech in quiet [% correctly perceived words at 50dB, 65dB and 80dB SPL].
- The benefit in self-reported hearing outcome when using the Investigational device at 3- and 6-months post-surgery compared to the unaided hearing assessed by:
 - The improvement in scores using the Abbreviated Profile of Hearing Aid Benefit (APHAB).
 - The improvement in scores using the Speech, Spatial and Qualities of Hearing Scale (SSQ).

- The benefit in health-related quality of life (HRQoL) measured by the difference in scores with HUI when using the at 3 and 6-months post-surgery compared to the pre-operative hearing situation.
- Surgical information:
 - Soft tissue thickness
 - Surgery time
 - Bone polishing/removal at the actuator site
 - BI300 Implant length
 - Location of BI300 Implant
 - Type of anaesthesia
 - Soft tissue reduction
 - Surgical incision type
 - Length of the surgical incision
 - Placement of the coil
 - Location of the surgical incision in relation to the actuator
- Usage information:
 - Magnet choice
 - Sound Processor retention
 - Sound Processor wearing comfort
 - Use of SoftWear pad
 - Daily use
 - Daily streaming
 - Battery lifetime
- The difference in hearing performance between the Investigational device and to a Baha 5 Power Sound Processor on a Baha Softband (preoperative) assessed at fitting, 3- and 6-months post-surgery as:
 - The difference in Thresholds audiometry, free-field [PTA4, mean of 0.5, 1, 2 and 4 kHz].
 - The difference in Thresholds audiometry, free-field [0.25, 0.5, 0.75, 1.0, 1.5, 2.0, 3.0, 4.0, 6.0 and 8.0 kHz].
 - The difference in Adaptive speech in noise [signal-to-noise ratio, 50% speech understanding].
 - The difference in Speech in quiet [% correctly repeated words at 50dB, 65dB and 80dB SPL].
- BC Direct [0.25, 0.5, 0.75, 1.0, 1.5, 2.0, 3.0, 4.0 and 6.0 kHz] will be performed using a Baha Softband (preoperatively) at screening/baseline and using the Investigational device at fitting, 3- and 6-months post-surgery.

9.2.3 Tertiary Outcome measures

- The difference in hearing performance at fitting- 3- and 6 months post-surgery when using the Investigational device compared to a preoperative hearing aid (if used by the patient) assessed as:
 - The difference in Adaptive speech in noise [signal-to-noise ratio, 50% speech understanding].
- Feedback measurements to be collected the Investigational device.

9.2.4 Exploratory Outcome measures.

There are no exploratory Outcome measures.

9.3 Hypotheses

The hierarchical testing procedure below is introduced to guarantee that the probability of Type I error is < 2.5% for all confirmative statements. The order of the hierarchical testing procedure will be:

1. PTA 4 pre-operative unaided vs. 3 months post-surgery (Primary efficacy analysis)
2. Adaptive speech recognition in noise (50% performance), signal to noise ratio (SNR) pre-operative unaided vs. 3 months post-surgery
3. Speech in quiet at 65dB SPL pre-operative unaided vs. 3 months post-surgery
4. APHAB Global pre-operative unaided vs. 2 months post fitting aided
5. Hearing attribute (HUI) pre-operative situation vs. 3 months post-surgery
6. Mean of the 12 items (Total score) in the SSQ pre-op unaided vs. 3 months post-surgery

If the first analysis is significant the probability mass 0.025 will go to the second analysis. If the second analysis is also significant the probability mass 0.025 will go to the third analysis and so on. When the first non-significant analysis is reached this and all analyses thereafter will be non-confirmative while the previous analyses will be confirmative. If the first analysis is non-significant no analysis will be confirmative. All testing will be Alpha level of 0.025 and one sided test will be used and the analysis will be performed on the ITT.

9.3.1 Primary Hypothesis

Group mean free-field PTA4 (average of 500, 1000, 2000, and 4000 Hz) with the Investigational device at the 3-month postoperative interval will be improved over that measured preoperatively in the unaided condition (baseline).

This endpoint is represented by the following hypotheses:

$$H_0: \mu_F - \alpha_0 = 0,$$

$$H_a: \mu_F - \alpha_0 \neq 0,$$

where:

α_0 = baseline preoperative PTA4;

μ_F = mean follow-up PTA4 3 months postoperative.

Alpha level of 0.05 and two sided test will be used and the analysis will be performed on the ITT population.

Group mean Adaptive speech recognition in noise (50% performance), speech to noise ratio (SNR) with the Investigational device at the 3-month postoperative interval will be improved over that measured preoperatively in the unaided condition.

This endpoint is represented by the following hypotheses:

$$H_0: \mu_F - \alpha_0 = 0,$$

$$H_a: \mu_F - \alpha_0 \neq 0,$$

where:

α_0 = baseline preoperative Adaptive speech recognition in noise (50% performance), speech to noise ratio (SNR);

μ_F = mean follow-up Adaptive speech recognition in noise (50% performance), speech to noise ratio (SNR) 3 months postoperative.

Alpha level of 0.05 and two sided test will be used and the analysis will be performed on the ITT population.

9.3.2 Secondary Hypothesis

Group mean Speech in quiet at 65dB when using the Investigational device at 3 months postoperative compared to the unaided hearing.

This endpoint is represented by the following hypotheses:

$$H_0: \mu_F - \alpha_0 = 0,$$

$$H_a: \mu_F - \alpha_0 \neq 0,$$

where:

α_0 = baseline preoperative word recognition score;

μ_F = mean follow-up word recognition score 3 months postoperative.

Group mean Global score using the Abbreviated Profile of Hearing Aid Benefit (APHAB) when using the Investigational device at 3 months post surgery compared to unaided hearing.

This endpoint is represented by the following hypotheses:

$$H_0: \mu_F - \alpha_0 = 0,$$

$$H_a: \mu_F - \alpha_0 \neq 0,$$

where:

α_0 = baseline APHAB Global score;

μ_F = mean follow-up APHAB Global score 3 months postoperative.

Group mean Hearing attribute (HUI) when using the Investigational device at 3 months post surgery compared to the preoperative hearing situation.

This endpoint is represented by the following hypotheses:

$$H_0: \mu_F - \alpha_0 = 0,$$

$$H_a: \mu_F - \alpha_0 \neq 0,$$

where:

α_0 = baseline Hearing attribute (HUI);

μ_F = mean follow-up Hearing attribute (HUI) 3 months post-fitting.

Group mean Total score using the Speech, Spatial and Qualities of Hearing Scale (SSQ) when using the Investigational device at 3 months post surgery compared to the unaided hearing.

This endpoint is represented by the following hypotheses:

$$H_0: \mu_F - \alpha_0 = 0,$$

$$H_a: \mu_F - \alpha_0 \neq 0,$$

where:

α_0 = baseline SSQ Total score;

μ_F = mean follow-up SSQ Total score 2 months post-fitting.

All other secondary outcomes will not be formally hypothesis tested but summarized and p-values will be calculated as described in 9.1 General considerations.

9.3.3 Exploratory Hypothesis

There are no exploratory hypotheses.

9.4 Sample Size Determination

Based on 6 months safety data from 51 subjects implanted with the predecessor Osia System at 5 clinics in the multicentre clinical investigation described in section 4.2.2.1 (8) it is judged that approximately 10 subjects per clinic and 3 clinics is reasonable for detecting any safety issues with the Investigational device in this study. The primary safety evaluation will be performed 3 months post-surgery, which with an estimation of 30 subjects will equate 7.5 patient years. This is considered to be enough safety data for the primary safety analysis.

With a total of 30 subjects, there will be a very high power to detect significant changes in the primary performance evaluations *audiometric thresholds (PTA4)* and *adaptive speech in noise (speech to noise ratio, SNR)*.

PTA4: Assuming the same mean reduction in PTA4 as in the multicentre clinical investigation of the predecessor Osia System (Mean change -25 dB, SD 9.5 dB), the resulting power with 30 subjects is 0.99.

SNR: In the multicentre clinical investigation of the predecessor Osia System a change in SNR from 4.98 dB (SD 7.76 dB) unaided to -8.19 dB (SD 6.58 dB) aided resulted in a mean improvement in SNR of -13.3 dB (SD 8.1 dB). In that investigation, speech was presented from the front and noise from the rear speaker. In the present investigation, however, both speech and noise will be presented from the front speaker, which is known to result in higher SNR values in the aided situation (the SNR in the unaided situation is not expected to change significantly). In a pilot clinical investigation conducted at Cochlear's own research facility (CBAS5271, Sub study 118), a mean SNR value of -2.5 dB was recorded with the Investigational device (Osia 2 System). Assuming that in the present investigation the unaided mean SNR is similar to the unaided scores in the multicenter investigation and that the aided mean SNR is similar to the pilot investigation, a mean improvement in SNR of approximately -7.6 dB (SD 8.1 dB) is expected. With 30 subjects, the resulting power is 0.99.

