4.2.2.1.2 Safety

In total 68 *Adverse Events* (AEs) were reported during the first six months of the clinical investigation, whereof thirty-three (33) were judged as possibly, probably or causally related to the study device and/or procedure. Most of the AEs were reported as mild and related to post-operative pain or transient irritation/swelling.

Three (3) *Serious Adverse Events* (SAEs) were reported within the first six months and within the same subject. Two (2) of these SAEs were unrelated to the study device and/or procedure, and one (1) was related to the surgical procedure: One Osia Implant was removed due to wound infection starting shortly after surgery. There were no device-related SAEs recorded during this time period.

Seventy-one (71) *Device Deficiencies* (DDs) have been reported (to date); However, none of the DDs were related to the Implant (Fitting Software: 46.5%; Sound Processor: 41%; User Manual: 8.5%; Broken safety line: 4%)

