7.2.3 Number of Subjects Required

Thirty subjects are to be enrolled in the investigation, i.e. will receive the implant.

It is expected that approximately 33 subjects are to be screened to meet this sample size.

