## **3 STATISTICS**

### **3.1 Sample Size**

Based on 6 months safety data from 51 subjects implanted with the predecessor Osia System at 5 clinics in the multicentre clinical investigation described in section 4.2.2.1 it is judged that approximately 10 subjects per clinic and 3 clinics is reasonable for detecting any safety issues with the Investigational device in this study. The primary safety evaluation will be performed 3 months post-surgery, which with an estimation of 30 subjects will equate 7.5 patient years. This is considered to be enough safety data for the primary safety analysis.

With a total of 30 subjects, there will be a very high power to detect significant changes in the primary performance evaluations audiometric thresholds (PTA4) and adaptive speech in noise (speech to noise ratio, SNR) at 3 months.

**PTA4:** Assuming the same mean reduction in PTA4 as in the multicentre clinical investigation of the predecessor Osia System (Mean change -25 dB, SD 9.5 dB), the resulting power with 30 subjects is 0.99.

**SNR:** In the multicentre clinical investigation of the predecessor Osia System a change in SNR from 4.98 dB (SD 7.76 dB) unaided to -8.19 dB (SD 6.58 dB) aided resulted in a mean improvement in SNR of -13.3 dB (SD 8.1 dB). In that investigation, speech was presented from the front and noise from the rear speaker. In the present investigation, however, both speech and noise will be presented from the front speaker, which is known to result in higher SNR values in the aided situation (the SNR in the unaided situation is not expected to change significantly). In a pilot clinical investigation conducted at Cochlear's own research facility (CBAS5271, Sub study 118), a mean SNR value of -2.5 dB was recorded

with the Investigational device (Osia 2 System). Assuming that in the present investigation the unaided mean SNR is similar to the unaided scores in the multicenter investigation and that the aided mean SNR is similar to the pilot investigation, a mean improvement in SNR of approximately -7.6 dB (SD 8.1 dB) is expected. With 30 subjects, the resulting power is 0.99.

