#### **3.4.4.14 Adverse events**

Separate tabulations of AEs, ADEs, SAEs, SADEs and AESIs will be produced. AEs, ADEs and AESIs will also be produced by severity (mild, moderate or severe) and relationship (related defined as Possibly, Probably and Definitely related). Number of events, number of subject and percent with events by System Organ Class (SOC, CTCAE) and CTCAE term will be presented.

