#### **3.5.1 Timing of analyses**

The first reporting of analyses will be made when all patients have completed their 3 months visit of the data up to 3 months. This analysis is regarded as the primary analysis. At the end of the study, at 6 months, the second and final reporting of the study will be made including all data up to the 6 months visit including data prior to the 3 months visit (ie all data in the study).

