### **3.7 Presentation of data**

#### **3.7.1 General**

All data will be presented in summarized tables. The distribution of continuous variables as well as change in continuous variables will be given as n, mean, SD, SEM, Median, Min and Max and the distribution of dichotomous and categorical variables will be given as number and percentages. For continuous variables estimated mean and the 95% two-sided confidence interval (bootstrapped) for difference between groups will be presented. The hypotheses' p-values and the corresponding/accompanying estimated with a 95% Ci will be presented where applicable.

Selected variables will be presented in figures showing either box plots or mean (95% CI) over time on actual values and/or change. Audiogram data will be presented as traditional audiograms.

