Table 14.2.11.1	Adaptive speech recognition in noise and Speech in quiet Osia System vs Softband (ITT Population)
Table 14.2.11.2	Adaptive speech recognition in noise and Speech in quiet Osia System vs Softband (PP Population)
Table 14.2.11.3	Adaptive speech recognition in noise and Speech in quiet Osia System vs Softband (landscape layout) (All patients - ITT Population)
Table 14.2.11.4	Adaptive speech recognition in noise and Speech in quiet Osia System vs Softband (landscape layout) (Mixed/Conductive patients - ITT Population)
Table 14.2.11.5	Adaptive speech recognition in noise and Speech in quiet Osia System vs Softband (landscape layout) (SSD patients - ITT Population)
Table 14.3.1.1	Summary of Adverse Events (Safety Population)
Table 14.3.1.2	Adverse Events (AE), by CTCAE SOC and CTCAE Term (Safety Population)
Table 14.3.1.3	Adverse Device Events (ADE possibly, probably and definitely related), by CTCAE SOC and CTCAE Term (Safety Population)
Table 14.3.1.4	Serious Adverse Events (SAE), by CTCAE SOC and CTCAE Term (Safety Population)
Table 14.3.1.6	Adverse Events of Special Interest (AESI), by CTCAE SOC and CTCAE Term (Safety Population)
Table 14.3.2	Numbness (Safety Population)
Table 14.3.3.1	Device deficiency per visit (Safety Population)
Table 14.3.3.2	Device deficiency (number of events and subjects) (Safety Population)

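### Does the safety justification for 30 subjects need a stated detectable event rate?

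*Protocol*

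**What the plan says.** Protocol 9.4 opens the sample size section with safety. Drawing on six months of data from 51 recipients of the predecessor device at 5 clinics, it judges that "approximately 10 subjects per clinic and 3 clinics is reasonable for detecting any safety issues with the Investigational device in this study". It then converts 30 subjects followed to the 3-month primary safety evaluation into 7.5 patient-years and calls that sufficient. SAP 3.1 repeats the judgement, including that the number "is reasonable for detecting any safety issues with the Investigational device in this study". The number itself is fixed in protocol 7.2.3: "Thirty subjects are to be enrolled in the investigation, i.e. will receive the implant".

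The safety outputs are tabulations. SAP 3.4.4.14 states: "Number of events, number of subject and percent with events by System Organ Class (SOC, CTCAE) and CTCAE term will be presented". SAP 3.7.1 adds that "the distribution of dichotomous and categorical variables will be given as number and percentages"; the confidence intervals it plans are for continuous variables and for the estimates that go with hypothesis tests. SAP 3.2.1 marks pass/fail criteria as not applicable. SAP 3.5.1 plans a first report at 3 months, after which "the second and final reporting of the study will be made including all data up to the 6 months visit".

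**The concern.** The same section gives each of the two efficacy endpoints a mean, an SD and a power. Safety is listed first as a reason for 30 subjects, yet it gets only an exposure total, and an exposure total does not say which event rates could be seen. The word *any* sets no lower limit on rarity, and 30 subjects can easily miss an uncommon event. No confidence interval is planned for adverse event incidence, so no planned output would say what a zero or low count can exclude.

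The risk is one of interpretation. A reader who finds no explantations in 30 subjects, next to a claim that the study could detect any safety issue, might take absence as reassurance when a true incidence of several per cent remains compatible with the data.

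**Working it through.** **Inputs.** n = 30 implanted (protocol 7.2.3). The safety population is all surgically treated subjects (protocol 9.5, SAP 3.3.1). Primary safety evaluation at 3 months, final report at 6 months. No dropout rate is given, and subjects lost after surgery are not replaced (protocol 7.2.5). The 95% and 80% detection levels below are conventional choices and do not come from the documents.

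**The plan's own figures.**
- Exposure: 30 × 3/12 = 7.5 patient-years, as stated. At 6 months, 30 × 0.5 = 15 if all complete.
- Power (paired t, two-sided 0.05): for speech in noise the noncentrality is 7.6/8.1 × √30 = 5.14, giving power 0.999; for PTA4 it is 25/9.5 × √30 = 14.4, giving power above 0.999. The stated 0.99 is met for both, so efficacy supports 30 subjects without help from the safety sentence.

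**What 30 subjects can show.** With independent subjects, all followed, P(at least one affected) = 1 − (1 − p)^30.

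| True incidence p | P(at least one in 30) |
|---|---|
| 1% | 26% |
| 2% | 45% |
| 5% | 79% |
| 10% | 96% |

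Solving for p:
- 95% detection: 1 − 0.05^(1/30) = 9.5%
- 90% detection: 1 − 0.10^(1/30) = 7.4%
- 80% detection: 1 − 0.20^(1/30) = 5.2%

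Exact two-sided 95% upper limit for 0/30: 1 − 0.025^(1/30) = 11.6%. For 1/30 the exact interval is 0.08% to 17.2%.

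**Sensitivity to follow-up.** If only 28 or 27 subjects reach 3 months (assumed), the 95% detection figure becomes 1 − 0.05^(1/28) = 10.1% or 1 − 0.05^(1/27) = 10.5%. The 6-month report adds time at risk but no subjects, so the per-subject bounds do not tighten.

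**Does anything in the plan use these quantities?** Protocol 9.10 and SAP 3.4.4.13 to 3.4.4.15 contain only tabulations. There is no safety hypothesis, no comparison with a reference rate, no acceptance limit and no interim analysis. Stating 9.5%, 5.2% or 11.6% would therefore change no sample size, test, population, existing table entry or decision.

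**Can a reader recover what is missing?** Yes. The planned tables give the number and percentage of subjects with events, and the exact interval follows from those counts and the denominator.

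**The case for a change.** The strongest case for a change is that a judgement offered as the sample size justification should show its basis, all the more because protocol 4.2.2 says no in-patient clinical data yet exist for the new system. The remedy looks cheap: a sentence on precision and one column of exact intervals in Table 14.3.1.1. The predecessor data are cited but no pooling or formal comparison of safety rates is specified, so they do not quantify what these 30 subjects add.

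Much of this stands. The sentence is broader than its support, no detectable rate appears anywhere, and the arithmetic above is right. Three things limit what follows from it.

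- *Any safety issues* can be read as whatever issues arise. Protocol 7.1.1 expects most of them to be surgical and early, and the predecessor study recorded 33 related events in 51 subjects over six months (protocol 4.2.2.1.2). Thirty subjects are enough to show problems that are that common.
- Safety oversight does not rest on a summary row. Protocol 8.4 provides for regular sponsor review of adverse device effects and deficiencies, 11.1.6 and 11.4.1 set 24-hour reporting for events of special interest and serious events, and 11.4.2 requires expedited sponsor assessment. None of this supplies a detectable rate, but it reduces the consequence of not stating one.
- Rewording protocol 9.4 is an amendment needing agreement and ethics committee notification (protocol 18). On the planned timeline (start August 2019, 4 to 6 months' enrolment), recruitment would have ended before the SAP date of 26 March 2020.

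The predecessor explantation ("One Osia Implant was removed due to wound infection starting shortly after surgery") does not strengthen the case. One in 51 has an exact 95% interval of 0.05% to 10.4%, and over that range the chance of seeing such an event in 30 subjects runs from 1.5% to 96%.

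**Conclusion.** The observation is accurate but calls for no change. The safety rationale is an unquantified judgement with one over-broad word; it is not a wrong figure. For a descriptive safety objective in a 30-subject device study, leaving out a detectable rate is a gap that the analysts and readers of the report can fill from the planned counts.

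Its size, if all 30 subjects are followed and are independent: 95% detection at about 9.5% incidence, 80% at about 5.2%, and an upper limit of 11.6% for a zero count. These bounds loosen slightly with dropout (10.1% to 10.5% for 95% detection with 28 or 27 subjects), and here *detection* means seeing at least one affected subject, not showing an excess over the predecessor. Whoever writes the report may give exact intervals beside the adverse event percentages, using the number actually followed. That is a presentational choice, and neither the efficacy conclusions nor any safety decision in the plan depends on it.
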